Official Title: A web-based intuitive eating intervention for young women with disordered eating: A pilot randomized controlled trial

NCT number: not yet assigned

Date of document: 2/15/2021

Introduction

Over the past 20 years, average adult weight and BMI has risen in the United States (U.S.), sparking a rise in public and private efforts to improve health via weight loss and dietary change [17, 20, 21]. Though a great deal of time and money has been dedicated to this, average BMI has not decreased and health has not improved [2, 4, 27, 29, 33]. However, the fight against weight gain has been linked to severe unintended consequences including weight cycling, distraction from health goals, increased rates of weight stigmatization, body dissatisfaction, disordered eating, and even death from extreme diets, eating disorders, weight loss surgery complications, and suicide related to these issues [2, 4, 29, 33].

Particularly, increased rates of eating disorders and disordered eating (DE) resulting from this weight-centric paradigm warrant further attention. Eating disorders carry the highest mortality rate of any mental illness, and are associated with high morbidity and societal burden [11, 12, 18, 28]. In 2019, over 10,000 people died from an eating disorder, and from 2018 to 2019 eating disorders cost the U.S. healthcare system approximately \$64.7 billion [12]. In the past 20 years, the lifetime prevalence of eating disorders in the U.S. has more-than doubled [19]. Parallel to the upsurge in eating disorders, the prevalence of DE, a subclinical pattern of maladaptive eating behavior, has also increased [30, 31]. DE is the greatest predictor for the development of an eating disorder [28]. DE disproportionately affects women, particularly young women [31, 41]. Currently, DE affects about 75% of U.S. women, most of whom will never receive treatment [7, 25, 31].

Concern for the lack of success and unintended consequences of a weight-centric paradigm has inspired calls for a shift in the promotion of healthy eating behavior. Given the high prevalence of DE, promotion of healthy eating ought to focus on this. At the forefront of this is Intuitive Eating (IE), a weight-neutral approach. The philosophy of IE posits that humans are born with the ability (an “intuition”) to self-regulate appetite and make dietary choices based on internal hunger and fullness cues, but external messaging about food and body size undermines this ability and causes distress and disorder around food [35, 37]. IE is characterized by attending to internal bodily cues, and flexible thinking and behavior concerning food [35, 37]. The Intuitive Eating Scale (IES-2) provides a way to quantify IE as a construct by measuring respondents’ ability to tune into various internal bodily cues [35]. In this scale, IE is broken down into 4 principles: Unconditional Permission to Eat (UPE), Reliance on Hunger and Fullness Cues (HFC), Eating for Physical Rather than Emotional Reasons (PRE), and Body-Food Choice Congruence (BFCC) [37]. Each principle is a measurable component of this style of eating; UPE is the absence of guilt or shame around eating, HFC is the ability to eat when hungry and stop when full, PRE is the ability to distinguish between physical and emotional hunger cues, and BFCC is the ability to eat in ways that are congruent with positive physical and emotional sensations and outcomes [35, 37]. These abilities are not static, though; several intervention studies have demonstrated individuals’ ability to learn how to eat intuitively e.g. [7, 10, 40].

A systematic literature review of 16 IE interventions found consistent decreases in DE, depression, and increases in self-esteem [9]. While all interventions included in this review yielded improved relationship with food, mixed results were shown for weight loss, dietary changes, and physiological indicators of health [9]. Another review of 20 IE interventions demonstrated similar findings [34]. Across interventions, there were overall decreases in depression, anxiety, restriction, body dissatisfaction, and drive for thinness, and increases in self-esteem and quality of life [34]. Measures of improved physiological health including weight loss, lowered blood glucose, and lowered cholesterol levels had less data support [34].

Likewise, research examining correlates of IE reliably suggests that IE is associated with lower rates of DE, lower body preoccupation, internalized weight stigma, and rates of depression, and greater self-esteem, and quality of life [6, 7, 9, 10, 15, 34, 39, 40]. Moreover, some studies have linked IE to improved dietary quality, weight stability, and lower BMI [1, 3, 14, 16, 22, 24, 26, 32, 36, 39].

Recently, an eight-year study following 1,491 participants demonstrated strong and lasting effects of IE [15]. This study followed participants from early adolescence to young adulthood and found that both baseline levels of IE and change in IE over time predicted lower odds of depression, low self-esteem, body dissatisfaction, unhealthy weight control behaviors (fasting, skipping meals), extreme weight

control behaviors (diet pills, purging), and binge eating at follow-up [15]. The data seems to suggest that IE is a protective factor for developing DE.

Though there is strong evidence suggesting that IE is associated with lower levels of DE, few studies have examined the effect of learning to eat intuitively for people with DE. One recent study tested an uncontrolled pilot feasibility trial of a brief IE intervention for college women with DE [7]. Seventy-one women with DE participated in this first-of-its-kind intervention, demonstrating that this population can learn to eat intuitively and benefit from it [7]. Participants had medium to large improvements in IE, body appreciation, and life satisfaction, as well as reductions in DE, body dissatisfaction, and weight-bias internalization [7].

This present study is the first randomized controlled trial (RCT) testing an IE intervention for DE. This study tested various health outcomes in a web-based intervention provided to a sample of young women with DE. Participants were assessed before (time 1/T1) and after (time 2/T2) completing the intervention. T1 to T2 changes in IE, DE, body appreciation, psychological flexibility, dichotomous thinking around food, and food intake were assessed.

Study Aims & Hypotheses

This study's aims were as follows: **Aim 1:** To introduce IE to a group of women with high levels of DE and assess associated outcomes. **Hypothesis 1:** When compared to the control group, the treatment group will experience the following changes from T1 to T2: **(a)** Increase in levels of IE, as measured by the Intuitive Eating Scale (IES-2), **(b)** Decrease in levels of DE, as measured by the Revised Three-Factor Eating Questionnaire (TFEQ-r18), **(c)** Increase in body appreciation, as measured by the Body Appreciation Scale (BAS-2), **(d)** Increase in psychological flexibility, as measured by the Acceptance and Action Questionnaire (AAQ-2), **(e)** Decrease in dichotomous thinking around food, as measured by the Dichotomous Thinking Scale (DT). **Aim 2:** To elucidate the effect of IE on food choice. **Hypothesis 2:** When compared to the control group, the treatment group's intake of fruits and vegetables, as measured by the NHANES Food Frequency Questionnaire, will increase from T1 to T2. **Hypothesis 3:** At baseline, IE will correlate with greater fruit and vegetable intake.

Method

Sample Characteristics

Participants were women ages 18-30 from the United States and Canada with high levels of DE, defined as higher-than-average scores (score > 25) on the TFEQ-r18, without a current eating disorder diagnosis, who have never previously participated in a formal intervention or course on IE (n=123). BMI at baseline ranged from 16.3 to 65. The sample was largely college-educated, white, and heterosexual (Table 1).

Potential participants were recruited via social media and online forums, including Facebook, Instagram, Tumblr, and Reddit. Recruited participants were asked to send the study screener to others who may be interested in participating, as well. Five-hundred-thirteen completed the screener, where 390 were excluded. Some met multiple criteria for exclusion, though none were excluded for having low TFEQ-r18 scores (Figure 1).

All participant information was deidentified, and contact information was kept in a separate secured file. Each participant was assigned a unique code used to connect data from different timepoints.

At Time 1 (T1), participants were randomly assigned to either a treatment (n=62) or waitlist control group (n=61). In most aspects, the groups were not significantly different at baseline (Table 1).

Procedures

IRB approval was granted from Western IRB on April 8th, 2020 (WIRB Tracking ID 20200516). After participants were recruited, the intervention began on April 29th, 2020 and concluded July 1st, 2020.

The intervention was a novel 10-week program aimed at promoting IE through pre-recorded videos, reading material, and bi-weekly discussion sessions. The intervention introduced the following

modules sequentially: Unconditional Permission to Eat, Reliance to Hunger and Fullness Cues, Body-Food Choice Congruence, Gentle Nutrition, and Joyful Movement.

Every other week, a new module was introduced. Participants were taught the concept of this module through video and reading, then prompted to practice it over the week. On opposite weeks, the module last introduced was discussed in greater detail through video, and participants were given the opportunity to discuss amongst one another and have all questions answered by the researchers. The intervention schedule included the following:

- *Week 1:* What is Intuitive Eating? A Program Overview and Introduction to Unconditional Permission to Eat (video + reading)
- *Week 2:* Discussion on Unconditional Permission to Eat, and Concerns about Eating Intuitively (video + discussion and questions/answer with researchers)
- *Week 3:* Reliance on Internal Cues: Eating when I'm Hungry & Stopping when I am Full (video + reading)
- *Week 4:* Discussion on Internal Cues, Concerns, and Questions Moving Forward -- It's OK to Make Mistakes (video + discussion and questions/answer with researchers)
- *Week 5:* Body-Food Choice Congruence: What Foods Make Me Feel Good? (video + reading)
- *Week 6:* Discussion on Food Choice -- How Do I Know if a Food Truly Makes Me Feel Good or if I Feel Good Because of Diet Culture Messages? (video + discussion and questions/answer with researchers)
- *Week 7:* Gentle Nutrition: Nourishing Yourself (video + reading)
- *Week 8:* Discussion on Nourishment, and Saying "NO" to the Food Police (video + discussion and questions/answer with researchers)
- *Week 9:* Joyful Movement: Find What Makes You Happy (video + reading)
- *Week 10:* Closing Discussion, and Final Questions (video + discussion and questions/answer with researchers)

Measures

Intuitive Eating Scale (IES-2)

The IES-2 was administered as a pre- and post-study measure of IE skills at T1 and T2. This 21-item scale measures the extent to which a respondent follows IE principles [37]. Response options are on a 5-point Likert-type scale, with 1=strongly disagree, 2=disagree, 3=neutral, 4=agree, 5=strongly agree. There are four subscales on this questionnaire, each measuring a separate aspect of IE: Unconditional Permission to Eat (UPE), Reliance on Hunger and Fullness Cues (HFC), Eating for Physical Rather Than Emotional Reasons (PRE), and Body-Food Choice Congruence (BFCC). Means are calculated for overall and subscale scores. A sample item is "*I trust my body to tell me when to stop eating*" [37].

National Health and Nutrition Examination Survey Food Frequency Questionnaire (N-FFQ)

The National Health and Nutrition Examination Survey Food Frequency Questionnaire (N-FFQ) was administered as a pre- and post-study measure of diet. The N-FFQ is a standardized food frequency questionnaire in which respondents are asked to recall their food and beverage intake from the past three days. It measures consumption of whole grains, refined grains, vegetables, greens, whole fruits, total fruits, total protein, plant protein, dairy, fat, sodium, added sugar, and alcohol [13].

Three-Factor Eating Questionnaire (TFEQ-r18)

The TFEQ-r18 was initially used as a screening tool, then was administered post-study at T2. Higher scores on this measure indicate greater levels of pathology and distress around eating. This 18-item measure is divided into three sub-sections, each measuring a different aspect of eating distress and pathology: cognitive restraint/restriction, uncontrolled/binge eating, and emotional eating. There are six questions for cognitive restraint/restriction, nine for uncontrolled eating, and three for emotional eating. Response options are on a 4-point Likert-type scale, with 1=definitely false, 2=mostly false, 3=mostly

true, 4=definitely true. Overall and subscale scores are calculated by summing item responses. One sample item is “*When I feel lonely, I console myself by eating*” [23].

Body Appreciation Scale (BAS-2)

The BAS-2 was used as a pre- and post-study measure of participants’ body appreciation. Body appreciation is an aspect of body image that specifically targets bodily respect and contentment. The BAS-2 is a 13-item questionnaire with 5-point Likert-type scale response options, 1=never, 2=seldom, 3=sometimes, 4=often, 5=always. One sample item is “*Despite its imperfections, I still like my body*” [38].

Acceptance and Action Questionnaire (AAQ-2)

The AAQ-2 was administered as a pre- and post-study measure of psychological flexibility. The AAQ-2 directly measures behavioral effectiveness as a proxy for psychological flexibility; this is one of the most common ways to measure psychological flexibility. There are seven items, with 7-point Likert-type scale response options, 1=never true, 2=very seldom true, 3=seldom true, 4=sometimes true, 5=frequently true, 6=almost always true, 7=always true. A sample item is “*I worry about not being able to control my worries and feelings*” [5].

Dichotomous Thinking Around Food Scale (DT)

The Dichotomous Thinking Around Food Scale (DT) was administered as a pre- and post-study measure of psychological flexibility specific to food. It is an 11-item measure of the extent to which respondents dichotomously categorize foods in an inflexible manner. Response options are on a 4-point Likert-type scale, 1=not at all true of me, 2=slightly true of me, 3=fairly true of me, and 4=very true of me. A sample item is “*I think of food as either ‘good’ or ‘bad’*” [8].

Analyses

All analyses were completed using SPSS v.21. The data were visually inspected and cleaned prior to running analyses. Independent Sample T-Tests were used to test baseline group differences. Correlations were run for other baseline data. To test the effect of the intervention, a 2x2 analysis of variance (ANOVA) was used.

Data Analysis Plan

Baseline correlations and pre- to post-study between groups analyses will be completed to test effects of IE. Correlation analyses will also be run testing associations between IE, body appreciation, psychological flexibility, dichotomous thinking around food, DE, subtypes of DE, BMI, and food choice broken down by food group. These analyses will utilize responses from all 123 participants.

At T2, 58.5% of the overall sample completed testing (n=72), including 51.6% of the treatment group (n=32), and 65.6% of the control group (n=40). Independent sample t-tests were run to compare treatment participants who completed the intervention to those who dropped out. At baseline, participants who completed treatment had higher levels of IE ($t=-2.11$, $p=.039$) and body appreciation ($t=-2.39$, $p=.02$), and lower levels of DE ($t=3.5$, $p=.001$) and dichotomous thinking ($t=2.68$, $p=.009$). There were no differences in treatment completion for participant age, race, nationality, sexual orientation, marital status, education, BMI, eating disorder history, or psychological flexibility.

To test the effect of participating in the intervention, a 2x2 ANOVA will be completed. Group x Time comparisons will examine T1 to T2 differences in the treatment and control groups.

[figure not shown]
Table 1. Participant Demographics x Group

	Overall (n=123)	Intervention (n=62)	Control (n=61)	p
Median Age (years)	25 ± 5	25 ± 4	25 ± 6	.917
Nationality				
United States	106 (86.2%)	51 (82.3%)	55 (90.2%)	.011*
Canada	17 (13.8%)	11 (17.7%)	6 (9.8%)	.011*
Race				
White	86 (69.9%)	48 (77.4%)	38 (62.3%)	.089
Asian	10 (8.2%)	6 (9.7%)	4 (6.6%)	.400
Latina	7 (5.7%)	1 (1.6%)	6 (9.8%)	.021*
Black	4 (3.3%)	1 (1.6%)	3 (4.9%)	.454
Other	2 (1.6%)	0 (0%)	2 (3.3%)	.153
2 or more races	14 (11.3%)	6 (9.7%)	8 (13.1%)	.454
Sexual Orientation				
Heterosexual	86 (69.9%)	47 (75.8%)	39 (63.9%)	.154
Homosexual	0 (0%)	0 (0%)	0 (0%)	1
Bisexual	33 (26.8%)	13 (21%)	20 (32.8%)	.141
Other	3 (2.4%)	2 (3.2%)	1 (1.6%)	.572
Prefer Not to Say	1 (0.8%)	0 (0%)	1 (1.6%)	.315
Marital Status				
Never married	87 (70.7%)	43 (69.4%)	44 (72.1%)	.738
Married	34 (27.6%)	18 (29%)	16 (26.2%)	.731
Divorced	1 (0.8%)	0 (0%)	1 (1.6%)	.315
Prefer Not to Say	1 (0.8%)	1 (1.6%)	0 (0%)	.323
Education				
High School or Equivalent	8 (6.5%)	3 (4.8%)	5 (8.2%)	.454
Trade School	1 (0.8%)	1 (1.6%)	0 (0%)	.323
Some College	19 (15.4%)	9 (14.5%)	10 (16.4%)	.776
Associate Degree	7 (5.7%)	2 (3.2%)	5 (8.2%)	.238
Bachelor's Degree	57 (46.3%)	32 (51.6%)	25 (41%)	.241
Master's Degree	28 (22.8%)	15 (24.2%)	13 (31.3%)	.706
Doctoral Degree	3 (2.4%)	0 (0%)	3 (4.9%)	.078
BMI (median)	27.8 ± 10.8	26.8 ± 9.6	29.9 ± 11.8	.044*

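### The only efficacy test, an unadjusted Group x Time ANOVA, in effect uses 72 of 123 randomised women, although treatment-arm dropout was related to baseline on four of the outcomes tested

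*Combined protocol and SAP*

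**What the plan says.** The Data Analysis Plan gives the follow-up counts: "At T2, 58.5% of the overall sample completed testing (n=72), including 51.6% of the treatment group (n=32), and 65.6% of the control group (n=40"). On efficacy it says "To test the effect of participating in the intervention, a 2x2 ANOVA will be completed" and "Group x Time comparisons will examine T1 to T2 differences in the treatment and control groups". The Analyses section names the same method and no other: "To test the effect of the intervention, a 2x2 analysis of variance (ANOVA) was used".

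On dropout, the Data Analysis Plan says "Independent sample t-tests were run to compare treatment participants who completed the intervention to those who dropped out". It reports "At baseline, participants who completed treatment had higher levels of IE" (t = -2.11, p = .039) and higher body appreciation (t = -2.39, p = .02), with lower DE (t = 3.5, p = .001) and lower dichotomous thinking (t = 2.68, p = .009). It adds: "There were no differences in treatment completion for participant age, race, nationality, sexual orientation, marital status, education, BMI, eating disorder history, or psychological flexibility".

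No covariate, analysis set, missing-data rule or sensitivity analysis is named for the efficacy test, and no completer-dropout comparison is described for the control arm. The opening paragraph of the Data Analysis Plan says that all 123 women contribute, but that sentence directly follows the one on correlation analyses.

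**The concern.** The four variables on which treatment-arm completers and dropouts differed are the outcomes of Hypotheses 1a, 1b, 1c and 1e. The plan thus documents selective loss on four of its five Hypothesis 1 outcomes and then specifies a test that takes no account of it.

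A Group x Time contrast subtracts the T1 score but does not condition on it. Women who stay because they began less severe tend to drift back toward the mean at T2, and an unadjusted change comparison counts that drift as a treatment effect. The drift cancels between arms only if selection was similar in both, and the control pattern is not reported.

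The sign is open too. Dropout driven by baseline severity makes treatment look worse and can hide a real benefit. Dropout of treatment women who did not improve pushes the other way and can create an apparent benefit. The evidence covers four outcomes: psychological flexibility showed no dropout difference, and food intake (Hypothesis 2) is not mentioned in the comparison.

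**Working it through.** **Inputs from the documents.** Randomised: 62 treatment, 61 control (Sample Characteristics). T2 data: 32 and 40. The four t-statistics quoted above (Data Analysis Plan).

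**Assumed, because the documents give no value.** T1-T2 correlation r of 0.5 or 0.7 (paired figures below are in that order); equal SD at T1 and T2; two-sided 5% test; the 32 treatment women with T2 data are those who completed the intervention.

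**1. Reproduce the plan's figures.** 72/123 = 58.5%, 32/62 = 51.6%, 40/61 = 65.6%: all match. Without T2: 30 + 21 = 51 women, 51/123 = 41.5%. The retention gap of 65.6 - 51.6 = 14.0 points is not itself significant (Fisher p = 0.14). With 32 + 30 - 2 = 60 degrees of freedom the t-statistics give p = .0390, .0200, .0009 and .0095, against the stated .039, .02, .001 and .009. They agree to rounding or truncation, which fits a comparison within the treatment arm.

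**2. Size of the completer-dropout difference.** d = |t| x sqrt(1/32 + 1/30). For DE: 3.5 x 0.2541 = 0.89.

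**3. Shift of the analysed treatment arm from the randomised one, in whole-arm SD.** Shift = d x (30/62) / sqrt(1 + d² x 32 x 30/62²). For DE: 0.430/1.094 = 0.39.

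**4. Bias with no true effect and random control dropout.** Expected bias is shift x (1 - r). For DE: 0.393 x 0.5 = 0.20 and 0.393 x 0.3 = 0.12. Simulated values are below (8,000 trials per setting, 62 v 61 women, bivariate normal scores, treatment retention logistic in T1 and calibrated to d). All are against treatment.

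| Outcome | d | Shift (SD) | Bias (SD), r = 0.5 / 0.7 |
|---|---|---|---|
| DE (TFEQ-r18) | 0.89 | 0.39 | 0.20 / 0.11 |
| Dichotomous thinking (DT) | 0.68 | 0.31 | 0.16 / 0.09 |
| Body appreciation (BAS-2) | 0.61 | 0.28 | 0.14 / 0.08 |
| Intuitive eating (IES-2) | 0.54 | 0.25 | 0.13 / 0.08 |

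Two-sided error is 12.6%/9.6% for DE and 8.0%/6.7% for IES-2. For DE nearly all of it is a false finding that treatment is worse (12.4%/9.0%); a false finding that it is better occurs in 0.3%/0.5%.

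**5. Control dropout with the same dependence on T1.** DE bias falls to 0.06/0.035 SD and error to about 5%. ANCOVA of T2 on arm and T1, in the same completers, has bias within 0.005 SD and error of 4.7% to 5.3% in all 16 null settings of steps 4 and 5.

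**6. Power for an assumed true DE benefit of 0.5 SD (4,000 to 6,000 trials).**

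| Control dropout | ANOVA | Completer ANCOVA |
|---|---|---|
| Random | 25% / 55% | 64% / 81% |
| Same pattern as treatment | 46% / 71% | 65% / 82% |
| No selection in either arm | 55% / 76% | 66% / 82% |

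The last row shows how much of the gap is ANCOVA's ordinary gain in precision.

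**7. Dropout that also depends on outcome.** Suppose treatment women whose T2 was worse than their T1 predicts also left. Baseline d is held at 0.89, control dropout is random and there is no true effect. Bias is in SD of DE; minus favours treatment.

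| Assumed completer-dropout gap in T2 given T1 (SD) | ANOVA | Completer ANCOVA |
|---|---|---|
| 0.25 | +0.10 / +0.04 | -0.11 / -0.09 |
| 0.5 | -0.01 / -0.05 | -0.22 / -0.18 |
| 0.89 | -0.14 / -0.16 | -0.37 / -0.30 |

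At a gap of 0.89, a false finding that treatment is better occurs in 8.5%/13.8% of trials with the ANOVA and 43%/41% with completer ANCOVA.

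**The case against.** The strongest objection comes from step 7. Under outcome-dependent dropout the completer ANCOVA is further from the truth than the ANOVA, so replacing one with the other is not safer under every mechanism. That is correct. But the ANOVA does better there only because two opposing biases partly cancel, which is no reason to rely on it. What stands is that conditioning on T1 is not enough alone, so a missing-not-at-random analysis has to accompany it.

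Second, the only mechanism that the documents evidence, dropout related to baseline, works against treatment, so the harm shown is lost power and not a false claim of benefit. This is true, and the reversed direction rests on an assumed outcome effect. Nothing in the plan excludes it.

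Third, the differences are imprecise. Approximate 95% intervals for d are 0.37 to 1.41 (DE), 0.17 to 1.19 (dichotomous thinking), 0.10 to 1.12 (body appreciation) and 0.03 to 1.04 (intuitive eating). The plan lists 13 comparisons, and at 0.05/13 = 0.0038 only DE remains. The evidence is therefore firm for DE and weaker for the others, although the imbalance among the women actually analysed exists whatever its p-value.

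Fourth, women who completed the intervention may not be exactly those who completed testing. The 60 degrees of freedom confirm 62 women, not a 32/30 split, so the sizes above depend on that assumption.

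Fifth, the statement about all 123 participants might be read as covering the efficacy test, and the flow diagram, which is not shown in the text available, may give numbers analysed. Neither supplies a method for 51 missing T2 scores.

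Last, this is a pilot and it discloses its attrition openly. It nevertheless tests directional between-group hypotheses, and the ANOVA is the only test of them.

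**Conclusion.** The concern holds and should be fixed before the efficacy results are relied on. For DE, dichotomous thinking, body appreciation and intuitive eating, the efficacy contrast is at high risk of attrition bias whose size and direction the plan cannot establish. With random control dropout and no true effect, the bias against treatment runs from 0.08 SD (intuitive eating, r = 0.7) to 0.20 SD (DE, r = 0.5). With similar control dropout it is small. With outcome-dependent dropout in the treatment arm it can favour treatment by 0.14 to 0.16 SD at the largest gap examined.

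The counts and t-statistics are the plan's own. The bias, error and power figures rest on the assumed correlations, normal scores, the assumed control-arm dropout pattern and the 32/30 split. The finding does not extend to psychological flexibility, and nothing can be said about food intake.

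**What to change.** - Make the main efficacy analysis one that conditions on T1: either ANCOVA of T2 on arm and T1, or a likelihood-based mixed model of T1 and T2 in all 123 women as randomised. Use the baseline predictors of dropout (IES-2, TFEQ-r18, BAS-2, DT) as covariates or auxiliary variables.
- State the analysis set and the missing-data assumption. Tie the sentence on all 123 participants explicitly to the baseline correlations, if that is what it means.
- Say whether completing the intervention and completing T2 testing describe the same women.
- Report completers against dropouts in both arms, including food intake.
- Add one missing-not-at-random sensitivity analysis, for example control-based imputation.
- Keep the ANOVA in the 72 completers as a labelled secondary analysis.

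**Cost.** No new participants or data: T1 scores exist, and for DE the T1 value is the screening score ("The TFEQ-r18 was initially used as a screening tool, then was administered post-study at T2"). The work is plan text and some analyst time. There are two drawbacks. The Analyses section already describes the ANOVA in the past tense and the dropout pattern has been seen, so the change must be labelled post hoc. The new estimate or interval may also be less favourable, by an amount that the documents do not allow to be stated.

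### The only planned effect test, Group x Time in a 2x2 ANOVA, is a valid change-score test; a supporting T1-adjusted ANCOVA would usually be more precise at almost no cost (optional).

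*Combined protocol and SAP*

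**What the plan says.** Hypothesis 1 (Study Aims & Hypotheses) is about change: "When compared to the control group, the treatment group will experience the following changes from T1 to T2". Hypothesis 2 takes the same form for fruit and vegetable intake. The Analyses section names one effect test: "To test the effect of the intervention, a 2x2 analysis of variance (ANOVA) was used". The Data Analysis Plan adds that "Group x Time comparisons will examine T1 to T2 differences in the treatment and control groups". No analysis that adjusts T2 for T1 appears anywhere.

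The documents do not state that Time is a within-person factor, but Sample Characteristics makes that the natural reading: "Each participant was assigned a unique code used to connect data from different timepoints". Every outcome has a baseline value. For disordered eating (DE) it is the screening score: "The TFEQ-r18 was initially used as a screening tool, then was administered post-study at T2".

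The Data Analysis Plan reports T2 data for 72 of 123 participants: 32 of 62 in treatment and 40 of 61 in control. On selective loss it says: "Independent sample t-tests were run to compare treatment participants who completed the intervention to those who dropped out". Treatment completers differed from treatment dropouts at baseline on intuitive eating, body appreciation, DE and dichotomous thinking. No matching comparison is given for control. Table 1 describes demographics, BMI and eating disorder history of all 123, and gives no T1 outcome means.

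**The concern.** In a randomised trial with one baseline and one follow-up measurement, analysing change is rarely the most efficient choice. Subtracting the whole T1 score over-corrects when T1 predicts T2 with a slope below 1, and this adds noise to the comparison. Only 72 participants can contribute, so wider intervals than necessary are a real price. The T1 scores needed to avoid it have already been collected.

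A reader also cannot see whether the analysed 32 and 40 started level on the outcomes. If they did not, the change-score and T1-adjusted estimates will differ in value as well as in precision.

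**Working it through.** **1. The plan's own figures.** 72/123 = 58.5%, 32/62 = 51.6% and 40/61 = 65.6%, as stated. Missing at T2: 51/123 = 41.5%. The completer-dropout t values of 2.11, 2.39, 3.5 and 2.68 on 60 df (32 v 30) give p = .0390, .0200, .0009 and .0095, which match the reported .039, .02, .001 and .009 up to rounding or truncation.

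**2. What Group x Time tests.** With two visits and Time within-person, the interaction F is the square of the unpaired t on T2 minus T1. In a generated data set of 32 v 40, both were 4.0870. The test needs both visits, so it uses at most 72 people. With no effect and no selection, both it and ANCOVA rejected in about 5% of simulated trials at two-sided 0.05.

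**3. Precision.** Set the T1 SD to 1 and the T2 SD to k, let rho be the T1-T2 correlation, and h = 1/32 + 1/40 = 0.05625.

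- Change score: variance = (1 + k² − 2·rho·k)·h, df 70.
- ANCOVA: variance = k²·(1 − rho²)·h·(1 + 1/68), df 69. The fitted slope is rho·k, and the factor 1 + 1/68 is the cost of estimating it.

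Example, k = 1 and rho = 0.5: change 1 × 0.05625 = 0.05625; ANCOVA 0.75 × 0.05625 × 1.0147 = 0.0428; reduction 23.9%.

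The documents give neither rho nor k, so both are assumed over a range. Reduction in variance from ANCOVA (negative = loss), dropout unrelated to T1:

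| k | rho 0.3 | 0.5 | 0.7 | 0.8 |
|---|---|---|---|---|
| 1 | 34.0% | 23.9% | 13.8% | 8.7% |
| 1.25 | 20.4% | 9.4% | 0.5% | −1.5% |
| 0.8 | 49.1% | 42.0% | 36.3% | 35.1% |

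At k = 1 the 95% CI half-widths, in T1 SDs, go from 0.560 to 0.455, 0.473 to 0.413, 0.366 to 0.340 and 0.299 to 0.286. The loss at k = 1.25, rho = 0.8 arises because the true slope there is exactly 1, so fixing it costs nothing.

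**4. Effect of selective dropout on the gain.** In simulation (62/61 randomised, 32/40 kept, random control loss), treatment-arm dropout was made to follow T1 strongly enough to give the t of 3.5 reported for DE. The reductions fall to about 30, 20, 9 and 4% at k = 1, and to 16, 5, −4 and −6% at k = 1.25. For DE the entry cut-off did not itself narrow the T1 spread, since "none were excluded for having low TFEQ-r18 scores".

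**5. Effect of selective dropout on the estimate (DE only).** Same set-up, no true effect, k = 1, rho 0.3, 0.5, 0.7, 0.8. If dropout follows observed T1, the change score is biased against treatment by 0.27, 0.19, 0.12 and 0.08 SD and ANCOVA is unbiased. If dropout follows the person's stable level, ANCOVA is biased toward treatment by 0.29, 0.21, 0.13 and 0.08 SD and the change score is unbiased. The 0.29 figure needs almost deterministic selection on the stable level (correlation about 0.93).

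**6. Does comparing the two results diagnose dropout?** No.

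- *Disagreement without selection.* By chance alone the T1 gap between arms has SD √0.05625 = 0.24. The two estimates then differ by about (1 − rho) times that gap, an SD of 0.17, 0.12, 0.07 and 0.05. For an assumed 0.5 SD effect, they fall on opposite sides of p = .05 in about 25, 18, 11 and 4% of simulated trials.
- *Agreement with harmful dropout.* If treatment-arm dropout follows the part of T2 not explained by T1 (assumed selection: that residual plus equal noise), with no true effect, both analyses are biased by about 0.47 SD at rho 0.5.

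**The case against.** The strongest objection is that the plan contains no error. The test is valid, it answers the hypotheses as worded, and an ANCOVA added now is probably post hoc: the Procedures section says the intervention ended in July 2020, and the Analyses section describes the ANOVA in the past tense. The gain rests on two unknown inputs and could be a small loss. The headline half of the variance needs both a low correlation and a shrinking SD. A completers-only ANCOVA also leaves the larger problem untouched, namely 48.4% v 34.4% lost. All of this stands, and it is why the point is optional. The silence on within-person Time and the lack of T1 descriptives are missing detail, and the point does not rest on them.

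Three stronger readings are tempting, and the documents do not support them.

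- A reader might infer that the planned ANOVA is wrong, or that ANCOVA is the correct analysis. Step 5 shows that either can be the biased one, and the documents do not say which kind of dropout occurred.
- A reader might infer that running both shows whether the answer depends on dropout. Step 6 shows that it does not.
- A reader might carry the step 5 biases over to every outcome. They are tuned to the largest reported t. The others are 2.11, 2.39 and 2.68; psychological flexibility showed no difference, and fruit and vegetable intake is not mentioned in that comparison.

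**Conclusion.** The point holds as a cheap, optional improvement. The planned test is a legitimate change-score comparison in at most 72 participants. A T1-adjusted ANCOVA on the same data would usually give narrower intervals: about 9 to 34% less variance with equal SDs and rho from 0.8 down to 0.3. The full range is from about 49% less (k = 0.8, rho = 0.3) to a 1.5% loss (k = 1.25, rho = 0.8), or a loss of up to about 6% if treatment-arm dropout follows T1 as strongly as the DE figure implies. All of this depends on assumed values of rho and k.

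Baseline imbalance between the analysed arms is neither shown nor excluded. That is a reason to print the T1 means, and it does not establish that the planned result is biased. The missing T2 data remain a separate problem under either analysis.

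**What to change.** Keep the planned Group x Time result. For every outcome in Hypotheses 1a-e and 2, add one supporting ANCOVA of T2 on group, with the T1 score of the same measure as the only covariate (the screening score for the TFEQ-r18). Report the adjusted difference with its 95% CI. Label it post hoc if T2 outcomes had already been analysed.

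Beside it, give T1 means and SDs of the analysed participants by arm. State that the two estimates will differ where those means differ. Do not present agreement as evidence that dropout is harmless, or disagreement as evidence of a particular dropout mechanism.

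The cost is one extra model per outcome in the same software and a short descriptive table, with no new data. The downside is a second result for each of at least six outcomes. To prevent selective use, report the ANCOVA for all of them and do not let it replace the planned test.
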